### 4.2.2 Secondary Endpoints

- Incidence of desensitisation to peanut in waiting list patients after receiving the active intervention (end of phase 2)
- Incidence of response to treatment(end of phase 1 (intervention group) and end of phase 2 (waiting list group))
- Fold and absolute increase in threshold (maximum tolerated peanut protein (mg))
- Change in quality of life (QoL) scores from baseline to the end of phase 1
- Change in QoL scores before and after immunotherapy (Baseline to phase 1(intervention group) or phase 1 to phase 2 (waiting list group).
- Change in immunological outcomes (Basophil histamine release, Peanut IgE, Total IgE, and skin prick test diameter (SPT))
- Change in severity of symptoms (World Allergy Organisation (WAO) score) from baseline to the end of phase 1

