### 5.4.1 Important Variable Definitions

- Peanut threshold (mg) – The no observed adverse effect level (NOAEL) – the highest cumulative dose of peanut that does not cause a reaction in a DBPCFC
- The lowest observed adverse effect level (LOAEL) is the lowest cumulative dose that causes a reaction (mg) in a DBPCFC
- Peanut IgE (kU/l 0 –1000) – Specific allergy antibody against peanut protein. Higher titres of IgE antibodies indicates higher probability of clinical allergy
- Basophil histamine release – Donor basophils stimulated in vitro by peanut extract at a range of concentrations. Basophil stimulation is detected by the mean fluorescent intensity of a cell surface marker (CD63). Area under the curve (AUC) of mean fluorescent intensity of CD63 (arbitrary units) and of the %CD63 positive cells against dose of peanut protein in milligrams.
- Tryptase (ng/ml) – a marker of background mast cell activation
- SPT diameter (mm 0–20) – A small amount of purified peanut is pricked on to the skin, and the diameter of the resulting wheal is recorded.

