### **9.2 Secondary Efficacy Analyses**

- The incidence of desensitisation to peanut in the waiting list group after receiving the active intervention (end of phase 2) will be reported and compared with the incidence of desensitisation to peanut in the intervention group (end of phase 1) using Fishers exact test.

- Incidence of response to treatment (i.e. desensitisation to the maintenance immunotherapy dose of 800mg) will be compared between the intervention and waiting list groups using Fishers exact test. Multiple logistic regression will be used to adjust the odds ratio of response to treatment for baseline characteristics described in section 7.2.
- The absolute and fold change in threshold will be compared within and between groups using paired and independent sample t-tests respectively. This may be extended to a linear regression adjusting for baseline covariates (section 7.2)
- QoL scores at the end of phase 1 will be compared between groups using a Mann Whitney U test.
- Change in QoL scores before and after intervention in both groups (Intervention: Phase1 – baseline; Waiting list: Phase 2– Phase 1) will be investigated within groups using a Wilcoxon sign rank test and then between groups using a Mann –Whitney U test.
- Change in peanut IgE from baseline to end of phase 1 will be compared between groups using a Mann–Whitney U test.
- Change in AUC (CD63MFI and %CD63 positive cells) of Basophil histamine release from baseline to end of phase 1 will be compared between groups using a Mann–Whitney U test
- Change in SPT results (peanut and other nuts) from baseline to end of phase 1 will be compared between groups using a Mann– Whitney U test
- Change in WAO score from baseline to end of phase 1 will be compared between groups using a Mann – Whitney U test

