### 13.1 Tables

Table Title	No.	Population	Endpoint	Time Points or how to conglomerate	Covariates or Subgroups	Summary Statistics	Formal Analysis
Summary of patient characteristics	1.1	Full analysis	Age	Baseline	Treatment	n, mean, SD	NA
			Sex			n, %	
			Weight			n, mean, SD	
			Asthma			n, %	
			Eczema			n, %	
			Rhinitis			n, %	
			Other food allergy			n, %	
			Tryptase			n, mean, SD	
			WAO score (historical)			n, median, range	
			Sensitisation to tree nuts			n, %	
			QoL score			n, median, range	
			Peanut specific IgE			n, median, range	
			Total IgE			n, median, range	
			Peanut SPT wheal diameter			n, mean, SD	
			Other nut SPT wheal diameter			n, mean, SD	
			Family history of peanut allergy			n, %	
			DBPCFC total peanut protein consumed			n, median, range	
DBPCFC peanut threshold (NOEL)	n, mean, SD						
DBPCFC WAO score	n, median, range						
DBPCFC LOAEL	n, mean, SD						

Basophil AUC of CD63MFI  
against peanut protein  
concentration

n, mean , SD

Basophil AUC of %CD63 positive  
cells against peanut protein  
concentration

n, mean, SD

Desensitisation to peanut after 6 months	2.1	Full analysis	Allergy desensitised or undesensitised	6 months	Treatment	n, %, odds ratio, 95% CI	Fishers exact test
					Treatment		
					Age		
					Sex		
					Asthma		
					Eczema		
					Rhinitis		
					Weight		
Logistic regression - adjusted odds of desensitised peanut allergy	2.2	Full analysis	Allergy desensitised or undesensitised	6 months	Sensitisation to tree nuts	odds ratios, 95% CI	Logistic regression
					Peanut specific IgE		
					Peanut SPT wheal diameter		
					Basophil AUC of CD63MFI against peanut protein concentration		
					QoL score		
					Family history of allergy		
					Baseline NOAEL		
Comparison of change in threshold between treatment groups	2.3	Full analysis	Threshold	Baseline and 6 months	Treatment	mean, SD, absolute and fold difference, 95% CI	t-test

Comparison of change in quality of life score between treatment groups	2.4	Full analysis	Quality of life score	Baseline and 6 months	Treatment	median, range, difference, 95% CI	Mann-Whitney U test
Comparison of change in quality of life score before and after intervention within and between treatment groups	2.5	Full analysis	Quality of life score	Baseline and 6 months (immunotherapy) 6 and 12 months (Waiting list)	Treatment	median, range, difference, 95% CI	Wilcoxon sign rank test Mann-Whitney U test

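### QoL is tested on end-of-phase scores although the endpoint is change from baseline; no continuous secondary outcome has a firm baseline-adjusted analysis, and raw fold change in threshold has no rule for a zero baseline

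*SAP*

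**What the plan says.** **QoL.** Section 4.2.2 lists as a secondary endpoint "Change in quality of life (QoL) scores from baseline to the end of phase 1". Table 2.4 in Section 13.1 is titled "Comparison of change in quality of life score between treatment groups", with baseline and 6 months as its time points. Section 9.2, however, says "QoL scores at the end of phase 1 will be compared between groups using a Mann Whitney U test". A further bullet there covers "Change in QoL scores before and after intervention in both groups"; it takes baseline to phase 1 in the intervention arm and phase 1 to phase 2 in the waiting list arm.

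**Other continuous or ordinal outcomes.** Section 9.2 says "Change in peanut IgE from baseline to end of phase 1 will be compared between groups" by a Mann-Whitney test. Basophil AUC, SPT and WAO score are handled in the same way. Total IgE has no bullet in Section 9.2 but appears in Table 2.6 with the same test.

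**Threshold.** "The absolute and fold change in threshold will be compared within and between groups using paired and independent sample t-tests respectively". A linear regression on the Section 7.2 covariates, which include baseline NOAEL, is offered only as something that may be done. Table 2.3 specifies mean, SD, absolute and fold difference, and a t-test. Section 5.4.1 defines threshold as "the highest cumulative dose of peanut that does not cause a reaction in a DBPCFC" and gives no rule for a value of zero.

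**General clause.** Section 9 permits transformations and non-parametric tests if assumptions fail. It names no trigger and no scale for any outcome.

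**The concern.** There are three linked problems.

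1. Section 9.2 contains no between-arm test of the QoL change endpoint that Sections 4.2.2 and 13.1 name. An analyst could defend either the end score or the change score from the SAP. Participants know their allocation (Section 5.3) and QoL comes from a questionnaire, so this choice should not remain open once data are visible.

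2. Baseline values are collected, and many of them enter the planned logistic models for the binary outcomes (Tables 2.2 and 2.8). Yet no continuous outcome is firmly assigned a model with its own baseline as covariate. Precision that costs nothing is left unused.

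3. A mean of raw fold changes gives a child with a very low starting threshold far more weight than one who starts higher, for the same clinical result. It has no value for a child whose baseline NOAEL is zero. The reported mean fold increase and its interval could then reflect a handful of children.

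**Working it through.** **The plan's own figure.** The SAP gives no precision or power figure for any continuous secondary outcome. Its only calculation is for the primary endpoint (Section 6: 64% against 30%, two-sided 5%, 90% power, Fisher's exact test). Exact enumeration gives power of 89.6% with 48 per arm and 90.6% with 49. Then 49/0.95 = 51.6, so 52 per arm and 104 in total. The SAP's figures reproduce, and 49 per arm is used below.

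**QoL passages side by side.**

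| Place | Quantity | Contrast |
|---|---|---|
| 4.2.2 | Change, baseline to end of phase 1 | (endpoint) |
| Table 2.4 | Change, baseline and 6 months | Between randomised arms |
| 9.2, QoL score bullet | End-of-phase-1 score | Between randomised arms |
| 9.2, before-and-after bullet | Change over each arm's own treatment period | Treated against later-treated |

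The last row serves a different endpoint. Both arms have had immunotherapy over the periods compared, so it is not the randomised comparison of treatment with avoidance.

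**Precision.** Assume equal SD σ at both times, correlation ρ between baseline and follow-up, and n per arm. The variance of the between-arm effect is (2σ²/n) × v, where:

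- end score: v = 1
- change: v = 2(1 − ρ)
- ANCOVA on baseline: v = 1 − ρ²

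Since 2(1 − ρ) − (1 − ρ²) = (1 − ρ)² ≥ 0, and 1 − ρ² ≤ 1, ANCOVA is never less precise than either alternative in large samples. Change is more precise than the end score only when ρ > 0.5.

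The SAP gives no ρ, SD or QoL effect, so the values of ρ and the 0.5 SD effect are assumptions. Power is Φ(0.5/√(2v/49) − 1.96). For example, with v = 1: 0.5/0.202 = 2.475, and Φ(0.515) = 70%.

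| ρ | v: end / change / ANCOVA | Power: end / change / ANCOVA |
|---|---|---|
| 0.3 | 1 / 1.4 / 0.91 | 70% / 55% / 74% |
| 0.5 | 1 / 1.0 / 0.75 | 70% / 70% / 82% |
| 0.7 | 1 / 0.6 / 0.51 | 70% / 89% / 93% |

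The ANCOVA standard error is 0.95, 0.87 and 0.71 times that of the end score, and 0.81, 0.87 and 0.92 times that of change. These formulas compare means; the planned Mann-Whitney tests will follow them only approximately.

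**Fold change.** Desensitisation is set at 1400 mg (Section 4.3). Section 5.3 uses 5, 50 and 200 mg as boundaries for the challenge-threshold strata. For a child who reaches 1400 mg:

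- from 200 mg: 1400/200 = 7-fold
- from 50 mg: 1400/50 = 28-fold
- from 5 mg: 1400/5 = 280-fold
- from 0: undefined

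Illustration: ten children all reach 1400 mg, nine from 200 mg and one from 5 mg. The mean fold change is (9 × 7 + 280)/10 = 34.3, and the one child supplies 280/343 = 82% of the sum. Without that child the mean is 7. The geometric mean of all ten is 7 × 40^0.1 = 10.1.

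Replacing a zero by an arbitrary value does not settle the matter: 1400/5 = 280 but 1400/0.5 = 2800, a tenfold difference produced by the substitute alone.

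**Power of the raw-fold t-test, by simulation with 49 per arm.**

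- Log-normal fold changes, shift of 0.6 log-SD (assumed): with log-SD 1, 1.5 and 2, the raw t-test has 66%, 47% and 32% power. A t-test on the log scale has 84% to 85%.
- A very large effect (64% of treated children reach 1400 mg, controls fluctuate around baseline, about 10% zero baselines replaced by 0.5 to 5 mg): the raw test rejects in at least 99% of runs.

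**The case against.** **Baseline is in fact used.** A reader might infer that no continuous secondary test uses baseline. The SAP does not support this. Peanut IgE, basophil AUC, SPT, WAO and threshold all use it through a change or ratio, and threshold has an optional regression. Only the QoL end-score test leaves it out.

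**End-score and change-score comparisons are valid under randomisation.** That is correct: preferring ANCOVA is an argument about efficiency, and its size depends on a correlation the SAP does not give. Nor can one say that the QoL end-score test loses precision against the stated change endpoint. At ρ = 0.3 the end score is the more precise of the two, and at 0.5 they tie. The QoL fault is the contradiction itself.

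**Fold change is partly protected.** One might infer that the threshold analysis breaks down, loses most of its power or drops the most sensitive children. The documents do not support that either. The parallel test of absolute change keeps children with a zero baseline, Section 9 allows a transformation or rank test for skewness, and power is hardly affected if the effect is very large. How many children have a NOAEL of 0 is unknown, and a recording convention may exist in the protocol. The SAP also does not say that the challenge stops at 1400 mg, so a ceiling on fold change cannot be taken as given.

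**What remains.** The general permission in Section 9 leaves the scale to be chosen after the data are seen, and no transformation of a ratio restores a zero denominator.

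**Conclusion.** The point holds in three parts of unequal strength.

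- **QoL mismatch: firm.** It rests only on the SAP's own text. Section 9.2 does not test the endpoint in Section 4.2.2 and Table 2.4, and no other bullet does so.
- **No firm baseline adjustment: a real but moderate loss of efficiency.** Over assumed correlations of 0.3 to 0.7, adjustment lowers the variance by 9% to 49% against the end score and by 35% to 15% against change. These figures assume equal variances and compare means, so they are a guide to the rank tests and not a measure of them.
- **Raw fold change: a fault of estimation first.** Table 2.3 fixes a mean, SD and t-test on a quantity that is undefined at zero and dominated by low baselines. The mean fold estimate and its interval are unreliable. The loss of power ranges from negligible to severe with the assumed effect and spread, so no single figure should be quoted.

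This should be corrected before analysis. It concerns secondary endpoints only and leaves the primary analysis and the sample size untouched.

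**What to change.** 1. **QoL:** make Sections 9.2 and 4.2.2 and Table 2.4 agree by comparing week-24 QoL between arms with baseline QoL as covariate. Keep the before-and-after analysis separate and label it as non-randomised.
2. **Peanut and total IgE (log scale), SPT and basophil AUC:** use the same baseline-adjusted comparison at week 24. Name in advance the outcomes expected to be non-normal and assign them a rank-based ANCOVA, so that the choice does not depend on the residuals. Use the rank-based form for the ordinal WAO score.
3. **Threshold:** analyse on the log scale, adjusted for baseline, with a pre-stated offset or rule for a NOAEL of 0. With an offset, the back-transformed ratio refers to the shifted quantity, and the report should say so. If the challenge stops at 1400 mg, add a sensitivity analysis treating that value as right-censored.
4. **Raw fold change:** report as median and range only, stating how many children have no defined value.

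Cost: revised wording, revised shells for Tables 2.3, 2.4, 2.6 and 2.7, and slightly more model checking. No new data are required.

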## 10 Safety Analyses

### 10.1 Extent of Exposure

The summary statistics will be produced in accordance with section 8.

### 10.2 Adverse Events

A table summarising the incidence of the following adverse events per peanut dose will be produced: mouth itching, abdominal pain, nausea, vomiting, diarrhoea, urticaria, angioedema, erythema, rhinitis, wheezing, laryngeal oedema, cardiovascular collapse, fainting, admission to intensive care unit (ITU), serious

adverse reaction, suspected unexpected serious adverse event (SUSAR), use of nebulised beta 2 agonist and use of intramuscular adrenaline.

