## 5 Study Methods

### 5.1 General Study Design and Plan

Single centre, randomized controlled trial of a novel active intervention (peanut oral immunotherapy) versus the status quo (peanut avoidance) in patients with peanut allergy. Two phase (package) design.

- Phase 1: Subjects randomly allocated (using minimisation methods – 80% chance of being assigned to imbalance minimising arm) to active intervention arm or waiting list arm. After 6 months all patients will be assessed for peanut allergy.
- Phase 2: Participants in waiting list arm still allergic to peanut at the end of phase 1 will be given the active intervention.

The figure below shows the study design.

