### 5.4 Study Variables

The visit schedule is shown below:

Week	0	Phase 1										Phase 2									
		2	4	6	8	10	12	14	16	18	24	26*	28*	30*	32*	34*	36*	38*	40*	42*	48*
Active immunotherapy visit	1	2	3	4	5	6	7	8	9	10	11	-	-	-	-	-	-	-	-	-	-
Waiting list visit*	(Baseline)	-	-	-	-	-	-	-	-	-	2	3*	4*	5*	6*	7*	8*	9*	10*	11*	12*
Demographics	x																				
Other allergies	x																				
WAO score (historical)	x																				
DBPCFC (NOAEL, LOAEL, WAO score)	x									x											x
Peanut SPT	x									x											x
Other nut SPT	x									x											x
Peanut specific IgE	x									x											x
Total IgE	x									x											x
Basophil histamine release	x									x											x
Tryptase	x																				
QoL questionnaire	x									x											x
OIT updose*		x	x	x	x	x	x	x	x	x	x	x	x	x	x	x	x	x	x	x	x

*\*Only waiting list patients who are not desensitised to peanut after 24 weeks undergo immunotherapy from week 26 to 48*

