### 7.1.3 Safety Population

All subjects who received any study treatment (including control) and are confirmed as providing complete follow-up regarding adverse event information.

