## 8 Summary of Study Data

Summaries of the study data will be presented as tables with separate columns for randomised group. All randomised patients will be included regardless of those who may not have completed the study. A table of baseline characteristics of patients will be included with a row for each covariate described in section 7.2.

Continuous variables will be summarised using means and standard deviations (or median and interquartile range if more appropriate) and categorical variables will be summarised using frequencies and percentages. The extent of missing data will be reported using annotations for the table and graphically using plots

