### 10.3 Deaths, Serious Adverse Events and other Significant Adverse Events

The summary statistics will be produced in accordance with section 8.

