Comparison of change in peanut immunological outcomes between treatment groups	2.6	Full analysis	Peanut IgE Total IgE Peanut SPT Other nut SPT Basophil histamine release CD63MFI (AUC) Basophil histamine release %CD63 positive cells (AUC)	Baseline and 6 months	Treatment	median, range, difference, 95% CI	Mann-Whitney U tests
Comparison of change in WAO score between treatment groups	2.7	Full analysis	WAO score	Baseline and 6 months	Treatment	median, range, difference, 95% CI	Mann-Whitney U tests
Predictors of treatment response	2.8	All patients who underwent immunotherapy	Response to immunotherapy	6 months (or 12 months for Waiting list group)	Treatment Age Sex Asthma Eczema Rhinitis Weight	odds ratios, 95% CI	Logistic regression

Sensitisation to tree nuts

Peanut specific IgE

Peanut SPT wheal diameter

Basophil AUC of CD63MFI against peanut protein concentration

QoL score

Family history of allergy peanut

Baseline NOAEL

Adverse events per dose	2.9	Safety population	Mouth itching Abdominal pain Nausea Vomiting Diarrhoea Urticaria Angioedema Erythema Rhinitis Wheezing Laryngeal oedema Cardiovascular collapse Fainting Admission to ITU Serious adverse reaction SUSAR	End of study	Treatment	n, %	NA
-------------------------	-----	-------------------	---	--------------	-----------	------	----

Use of nebulised beta 2 agonist

Use of intramuscular adrenaline

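### The only adverse-event table listed is per peanut dose, by treatment, at end of study; for the listed events it gives neither the share of children affected nor a phase 1 comparison with avoidance

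*SAP*

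**What the plan says.** - **SAP 10.2** plans one summary: "A table summarising the incidence of the following adverse events per peanut dose will be produced". The events range from mouth itching, vomiting and wheezing to intensive care admission, serious adverse reactions, nebulised beta 2 agonist use and intramuscular adrenaline use.
- **SAP 13.1** lists it as Table 2.9, "Adverse events per dose": safety population, end of study, split by treatment, n and %, no formal analysis. It is the only adverse-event table listed.
- **SAP 8** sets the general layout: "Summaries of the study data will be presented as tables with separate columns for randomised group". It asks for frequencies and percentages for categorical variables and includes all randomised patients.
- **SAP 10.3**, on deaths, serious and other significant adverse events, says only: "The summary statistics will be produced in accordance with section 8".
- **SAP 7.1.3** defines the safety population as "All subjects who received any study treatment (including control" arm, provided that adverse-event follow-up is complete.
- **SAP 5.1** compares immunotherapy "versus the status quo (peanut avoidance) in patients with peanut allergy". It then says: "Participants in waiting list arm still allergic to peanut at the end of phase 1 will be given the active intervention". The footnote to the visit schedule in **SAP 5.4** agrees: "Only waiting list patients who are not desensitised to peanut after 24 weeks undergo immunotherapy from week 26 to 48".
- **SAP 6** expects 35 waiting-list patients to go on to treatment in phase 2.

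**The concern.** Two safety questions matter to a family or clinician: what share of children had a given reaction, and how that compares with continued avoidance. Phase 1 is the only period in which randomised groups are on immunotherapy and on avoidance side by side.

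Table 2.9 answers neither question for the listed events. Its unit is the dose, and the waiting list takes no immunotherapy doses in phase 1. Its time point is study end, by which time most of the waiting list is expected to have been treated. By contrast, the between-arm tables for desensitisation, threshold, immunological outcomes and symptom severity (Tables 2.1 to 2.3, 2.6 and 2.7) are all cut at 6 months. The safety population includes the controls, but for most listed events no specified analysis makes use of their avoidance period.

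**Working it through.** **1. Reproduce the plan's figure for crossover.** Inputs from SAP 6: control desensitisation 30%, 49 per arm evaluable, 52 per arm randomised, 5% dropout.

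- The 49 per arm reproduces: exact power of Fisher's test for 64% v 30% is 0.906 at n = 49 and 0.896 at n = 48.
- Expected crossover = (1 − 0.30) × n. With n = 49 this is 34.3; with n = 52 × 0.95 = 49.4 it is 34.6. Both agree with the stated 35.
- Share of the waiting list treated by study end: 35/49 = 71% of evaluable children, 35/52 = 67% of those randomised.

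**2. The waiting-list column of Table 2.9.** Take per dose to mean per administered immunotherapy dose, and treatment to mean randomised arm, as section 8 implies.

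- Phase 1: immunotherapy doses = 0, so events/doses is undefined. The visit schedule shows peanut given to this arm only in the food challenges.
- Study end: every immunotherapy dose in this column was given in phase 2. The column therefore describes reactions to immunotherapy, as does the intervention column.

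**3. A per-dose figure does not fix the per-child figure.** The SAP gives no event rates and no number of doses per child, so the following is illustration only. Suppose 5 of 49 children have one event each.

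| Denominator | Calculation | Result |
|---|---|---|
| Children | 5/49 | 10.2% |
| The 10 phase 1 up-dose visits in SAP 5.4 | 5/(49 × 10) = 5/490 | 1.02% |
| Daily dosing for 24 weeks (assumed, 168 days) | 5/(49 × 168) = 5/8232 | 0.061% |

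The per-dose figure is 10 to 168 times smaller for the same events.

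In the other direction, assume 1% per dose and independent events. The share of children with at least one event is 1 − 0.99^10 = 9.6% with 10 doses and 1 − 0.99^168 = 81.5% with 168. If the same number of events fell in only 5 of 50 children, the share would be 10% in either case.

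**4. Crossover in a per-child summary at study end.** This bears on section 10.3. Let r be the assumed per-child risk on immunotherapy, a the risk on avoidance and f the share crossing over (35/52 to 35/49). The waiting-list risk by study end is 1 − (1 − a)(1 − f × r).

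| Assumed r v a | Phase 1 difference | Waiting-list risk by study end | Difference at study end |
|---|---|---|---|
| 20% v 2% | 18 points | 15.2% to 16.0% | 4.0 to 4.8 points |
| 50% v 5% | 45 points | 37.0% to 38.9% | 11.1 to 13.0 points |

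A summary by randomised arm with no phase cut would therefore hide most of the contrast with avoidance under these assumptions.

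**The case against.** **Section 10.3 covers part of the ground.** Taken with section 8, its natural reading gives numbers and percentages of participants by randomised arm, controls included, for deaths, serious and other significant events. The last group might take in adrenaline use or intensive care admission. A reader might infer from Table 2.9 that the trial could not report the share of children with a serious reaction, or that no safety analysis touches the control period. The document does not support either statement. What remains is that section 10.3 lists no table, does not define its third category and sets no phase cut, so step 4 applies to it. It does not evidently reach events such as vomiting or wheezing.

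**The wording of Table 2.9 is open.** Per peanut dose could mean by dose level, and treatment could mean treatment received. Either reading weakens part of the argument: a table by dose level might count children at each level. Neither supplies a comparison with avoidance, because a child on avoidance has no immunotherapy dose or dose level.

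**Per-dose incidence is a legitimate measure.** It says how often a dose provokes a reaction, and showing it for both treated groups is coherent. This stands; the fault is that it is the only table specified. Nor is the 10- to 168-fold gap a bias: it is the number of doses per child, a change of denominator applied to invented event counts.

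**Two further inferences should not be drawn.** One is that children who tolerate treatment well take more doses and so dilute the rate. The SAP gives one common up-dose schedule and no rule linking tolerance to the number of doses. The other is that a phase 1 comparison would be free of bias. SAP 5.3 says that participants are not blinded to their group, so reporting of itching, nausea or abdominal pain may differ between arms.

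**Conclusion.** The point holds for the listed events that section 10.3 does not clearly cover. The SAP fixes a unit and a time window that give neither the proportion of children affected nor a randomised phase 1 comparison with avoidance. This is a stated choice that serves the safety question poorly, not a detail left to the protocol.

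Its size is the 67% to 71% of the waiting list expected to be treated by study end, which rests on the SAP's own 30% control rate. The per-child and per-dose percentages rest on assumed events and dose counts, and show only how far the two measures can part.

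The loss of the per-child figure rests on reading per dose as per administered dose. The comparison of immunotherapy with immunotherapy rests on reading treatment as randomised arm. The missing comparison with avoidance holds under either reading of both terms. The primary analysis and the sample size are not affected.

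**What to change.** 1. Add an adverse-event table giving, for each listed event, the number and percentage of participants with at least one event and the count of events, by randomised arm, for phase 1 only (weeks 0 to 24).
2. Show waiting-list immunotherapy in phase 2 in a separate column.
3. Apply the same phase 1 cut to the section 10.3 summary and give it a table in section 13.1.
4. Keep Table 2.9 as a supplement restricted to immunotherapy periods. State its denominator and say whether treatment means randomised arm or treatment received.

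The cost is one extra table for the listed events and a listed table for a summary already promised. It depends on adverse events having been recorded during the avoidance period. Section 7.1.3 implies that they are, since it counts controls and requires complete adverse-event follow-up. However, the visit schedule shows no waiting-list visit between baseline and week 24, so the method of capture should be confirmed. The table should carry a note that reporting was open-label, which matters most for subjective symptoms.
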